3.2 Secondary Objectives (if applicable)

Secondary Objective : **Exploratory:** we will test whether loss of sleep-dependent spatial navigational memory at baseline is a predictor of cognitive decline at follow-up. A **linked objective** is to identify how the relationship between SWS/SWA and the rate of change in PiB uptake might be confounded by mPFC atrophy (for measures of SWS) and DWML volumes and DKI (for measures of PiB uptake).

4 Study Enrollment and Withdrawal

Subjects:

210 cognitively normal, ages 60-75, self-identified as African-American (150) or non-Hispanic white

CONFIDENTIAL

This material is the property of the NYU School of Medicine and Langone Medical Center. Do not disclose or use except as authorized in writing by the study sponsor

(60), Clinical Dementia Rating (CDR) of 0, ≥ -1.25 in global cognition z-scores from the WHICAP battery adjusted for race and education, English speakers, and with enough literacy to provide voluntary consent will be invited to participate.

Exclusion criteria at enrollment will be: intention to move from NYC within the same year, irregular sleep-wake cycles defined as ‘ ≥ 3 sleep episodes per 24-hr period’ or ‘day to day irregularity greater than 90 min. based on actigraphy, less than 5 or more than 10 hours of TST; OSA (defined as $AHI_4\% > 15$ and $AHI_4\% > 5$ with $Epworth \geq 10$); neurodegenerative disorders, history of early onset familial AD; insulin dependent diabetes; bipolar disorder, schizophrenia, intellectual disability or substance abuse; non-controlled pulmonary or cardiac diseases; brain tumors; stroke; head trauma and hydrocephalus.

Lifelong depression and anxiety will be allowed as long as there has been no active depressive episode within the last two years. Current use of any sedative/hypnotics or stimulants, gabapentin, pregabalin, tricyclic antidepressants, and trazodone or other psychoactive medications that may alter SWS. Stable (3 months or longer) use of antidepressants will be allowed. Caribbean or African-born blacks or subjects that don't fulfill inclusion criteria but express interest will be offered participation in similar NYU NIH-funded studies on sleep or normal aging.

Study Enrollment:

Self-identified AA and whites will be balanced by sex, age, BMI, income and education, and will live in the same NYC zip codes. Brooklyn will be the area of recruitment as it is the most ethnically diverse and largest most concentrated black population in the US -more than 900,000 blacks living in a 4-mile square area-. The sample will include self-identified African-American (AA) blacks and non-Hispanic whites. As described in our published methods^{158;166}, enrollment sites will include advertisements and collaborations with black-owned barbershops, beauty salons and churches that were part of our previous community studies in Brooklyn and other NYC boroughs. All advertisements and recruitment materials will be submitted for IRB approval prior to use. In addition, we will perform culturally-relevant educational events in senior centers and church health fairs. Recruitment will be implemented in consultation with a Community Activist ([name]) and a Community Advisory Board (CAB) that has been created for this cohort. It will include community stakeholders with whom we have long-standing relationships and consist of: black community leaders serving as Directors of Community-based organizations (CBOs) and members of the Brooklyn chapter of *CaringKind*. The CAB will comprise 8 members and will meet with the PIs and [name], who will be one of the lead members of the community advisory board every 2 months during year 1 and every 3 months thereafter. Once the award is made, it will discuss project goals, review recruitment strategies, refer individuals for participation and suggest new recruitment sites that might not have been available previously. Our success in assessing sleep in AAs is attributable to our sustained engagement efforts at the community level and help from former CABs.

Participating recruitment sites will be selected based on visibility, accessibility, safety, longevity and cooperativeness²⁰⁴. Preference will be accorded to those providing private room for interactions with subjects. Recruitment procedures will be discussed with site owners before scheduled visits. Respective owners will introduce the recruitment team, who will then approach potential participants (while waiting at the salon, after church services or senior center activities) to describe the protocol. The recruitment team will be made up of research coordinators and other members of the study staff. As in our previous interventions¹⁵⁸, staff will begin by exchanging pleasantries with potential participants followed by an introduction to the study.

If interested, eligibility will be confirmed and consent obtained. They will then complete the Center for Epidemiologic Studies Depression (CES-D)²⁰⁵ Scale, the Medical Outcomes Study Short Form (MOSSF)²⁰⁶, the ARES-TM questionnaire¹⁴⁹, a medication list and the AD8²⁰⁷ (these forms will be used for initial screening; interested subjects not eligible or with high risk for OSA will be offered participation in similar NYU NIH-funded studies). Those refusing to enroll will receive standard sleep literature and access to the NYU ADC Center or Brooklyn's NYU affiliated Lutheran Medical Center. No further contact will be made. During the first 9 months, themes derived from focus groups (*ROI MD004113*) and through meetings between the PIs, [name] and the CAB will be used to develop sleep and memory health booklets using Taylor's model²⁰⁸. These booklets will be left on the participating centers for recruitment outside the scheduled visits. All recruitment materials will be submitted to the IRB through a modification for approval

CONFIDENTIAL

This material is the property of the NYU School of Medicine and Langone Medical Center. Do not disclose or use except as authorized in writing by the study sponsor

before use.

4.1 Inclusion Criteria

In order to be eligible to participate in this study, an individual must meet all of the following criteria:

- Male and female subjects with normal cognition and ages 60 to 75.
- Within normal limits on neurological and psychiatric examinations. All subjects enrolled will have both a CDR=0, a MoCA > 25 and ≥ -1.25 in global cognition z-scores from the WHICAP battery.
- An informed family member or life-partner (preferably bed-partner) will be interviewed over the phone or on the first or second visit to confirm the reliability of the subject interview. A study partner is preferably a spouse, close friend, or relative.
- Self-identified as African-American Black or non-Hispanic white.
- All subjects must sign the Alzheimer's Disease Center consent form

4.2 Exclusion Criteria

An individual who meets any of the following criteria will be excluded from participation in this study:

- History of brain tumor, MRI evidence of brain damage or brain disease including significant trauma, hydrocephalus, seizures, mental retardation or other serious neurological disorder (*e.g.* Parkinson's disease or other movement disorders). Subjects with a Fazekas scale >2 will be excluded²⁶⁰.
- Significant history of alcoholism based off of the CAGE questionnaire (>2) or drug abuse.
- History of psychiatric illness (*e.g.*, schizophrenia, bipolar or PTSD)
- Lifelong depression and anxiety will be allowed as long as there has been no active depressive episode within the last two years.
- Geriatric Depression Scale²¹² (short form)>6.
- Insulin dependent diabetes.
- Evidence of clinically relevant cardiac, pulmonary, endocrine or hematological conditions based off of the PI's discretion.
- Physical impairment of such severity as to adversely affect the validity of psychological testing.
- Any prosthetic devices (*e.g.*, pacemaker or surgical clips) that constitutes a hazard for MRI imaging.
- Medications affecting cognition or SWS:
 - Narcotic analgesics.
 - Chronic use of medications with anticholinergic activity.
 - Anti-Parkinsonian medications (carbidopa/levodopa, amantadine, bromocriptine, pergolide, selegiline).
 - Others: amphetamines, amphetamine-like compounds, appetite suppressants, phenothiazines, reserpine, buspirone, clonidine, disulfiram, guanethidine, MAO inhibitors, theophylline, tricyclic antidepressants, gabapentin, pregabalin, trazodone, cholinesterase inhibitors, memantine.
- Chronic use of antidepressants are allowed.
- History of a first-degree family member with early onset (age <60 years) dementia.
- Irregular sleep-wake rhythms (based on participant self-report), short sleepers (< 5 hours a day) and long sleepers (> 10 hours a day).
- OSA (defined as AHI4%>15 and AHI4%>5 with Epworth \geq 10)
- Self-identified as US-born Caribbean Black, Caribbean-born Black or African-born Black.

Diagnostic Criteria:

1. The diagnoses of MCI, and AD. All subjects get extensive baseline and follow-up evaluations to identify co-morbidity and any confounding medical, neurological, and psychiatric conditions that can affect cognition. For all subjects, the study neurologist or psychiatrist administers a standardized interview of a knowledgeable informant. The diagnosis is assigned at consensus case conferences using established and reliable procedures. The following diagnoses might be given at follow-up:

CONFIDENTIAL

This material is the property of the NYU School of Medicine and Langone Medical Center. Do not disclose or use except as authorized in writing by the study sponsor

b. **The definition of MCI:** subjects demonstrating functional complaints (self-reported and supported by a knowledgeable informant) and who on clinical interviews show no dementia but with a CDR=0.5, GDS =3, and MOCA <25 are classified as MCI. Amnesic (a) aMCI is defined on the basis of updated Petersen criteria with delayed recall performance below 1.5 SD from age norms on 2 of the 3 tests within the delayed recall domain. Prior experience shows that the aMCI will likely also show deficits in other cognitive domains. The category of non-aMCI is defined based on performance on more than one cognitive test from a domain other than delayed recall, falling below $z=1.5$ SD from the norms (see below). Subjects judged to be cognitively impaired by the clinician, but with a presentation, tests, symptoms and clinical evaluation that is not consistent with MCI will be classified as 'Impaired, not MCI'.

c. **The diagnosis of AD:** at the follow-up is consistent with the NINCDS-ADRDA workgroup recommendations and DSM IV criteria. The definition of AD requires that after ruling out other dementia etiologies that the individual demonstrate on structured clinical interviews, progressive impairments in two or more areas of cognition and difficulties in activities of daily living. Thus AD is rated as CDR >0.5. The memory impairment criterion is satisfied by scores in the impaired range on any of the delayed recall tests in the neuropsychological battery. Functional impairment is estimated by scores on the Lawton Brody Activities of Daily Living Scale, the clinical history evaluation, and the informant interview.

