Brief Summary	African-Americans (AAs) have an increased prevalence of both Alzheimer's disease (AD) and vascular risk factors for AD such as diabetes and hypertension when compared to whites. However, in a recent community based study of non-demented elderly, black race was associated with higher amyloid burden after adjusting for vascular risk factors, suggesting the presence of additional physiological differences on AD-risk by race in the early stages of the disease. The purpose of this study is to test whether poor slow wave sleep (SWS) quantity (SWS duration) and quality (slow wave activity, SWA) is one of these physiological factors. To test these hypotheses, we will perform community outreach in barbershops, churches and senior centers in Brooklyn and other NYC boroughs with which we have created substantial ties in recent years. In consultation with community stakeholders, we will recruit 150 cognitively normal AA elderly (age 60-75) and 60 age, sex, BMI, income and education matched non-Hispanic whites from the same geographical areas. We will first perform a medical and cognitive evaluation (Visit 1). Participants will then undergo 2 nights of home sleep monitoring using an unattended device to exclude OSA, followed by 7 days of actigraphy with a sleep log to record sleep duration. Both devices will be returned by mail. Subjects with reported total sleep time (TST) between 5 and 10 hours and absence of moderate to severe OSA will be invited to perform a 2-night nocturnal polysomnography (NPSG) (Nights 1-2) and a PiB-PET MR scan (Visit 2).
Objectives	Objective 1: To test if African ancestry (%AF) is associated with short SWS duration and poor SWA in older AAs. Objective 2: To test the effect of race and its interaction with baseline short SWS duration/poor SWA on longitudinal amyloid deposition. Objective 3: To test the effect of race and baseline poor SWA on cognition. Secondary Objective 2.1: To test whether loss of sleep-dependent spatial navigational memory at baseline is a predictor of cognitive decline.
Methodology	30-36 month longitudinal study
Endpoint	Primary endpoint is longitudinal increase in amyloid deposition
Study Duration	5 years
Participant Duration	30-36 months

CONFIDENTIAL

[figure not shown]
This material is the property of the NYU School of Medicine and Langone Medical Center. Do not disclose or use except as authorized in writing by the study sponsor

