Approximately 20% of healthy adults have mild and 6.6% moderate-to-severe obstructive sleep apnea (OSA)⁸¹, with a higher incidence occurring in the elderly⁸². AAs generally show a higher prevalence of OSA³³⁻³⁶. Specifically, in the Cleveland Family Study, AAs presented with OSA at a younger age³⁵, while Ancoli-Israel et al.³⁴ found that older AAs were 2.5 times more likely to have severe OSA. These findings are in agreement with another study of adults aged 40-60, where OSA rates were higher among minorities³³. In contrast, both the Sleep Heart Health (7% AAs) and Scharf's et al. studies failed to show higher rates of OSA in AAs after controlling for obesity^{83;84}. However, AAs from these studies suffered more excessive daytime sleepiness, in agreement to previous findings suggesting that OSA-associated symptoms might be more common in AAs^{34;85}. Apnea occurs less commonly during SWS, as SWS is associated with a higher respiratory arousal threshold^{86;87} and more stable breathing⁸⁸. However, beyond a certain threshold of frequency, apnea in any sleep stage impairs entry into SWS. In addition, the temporal course of slow wave activity (SWA) has shown to be slower in mild OSA⁸⁹, and severe OSA patients show up to a 40% rebound in SWS duration during treatment with CPAP⁹⁰. All the above findings suggest that changes in SWS are common in OSA patients. SWS disruption may therefore be another mechanism by which OSA increases AD risk⁹¹⁻⁹³.

In summary: certain ethnic groups are more likely to have disturbed sleep. AAs show clear independent differences in SWS characteristics but not in sleep duration or OSA prevalence when compared to whites, after controlling for socioeconomic factors, obesity or health care behaviors. These differences seem unrelated to other explanatory factors (except for the partial effect of psychosocial stressors) and suggest that AAs may have less restorative sleep than whites. The brain consequences of these decreases in SWS are not known.

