
Ambulatory home monitoring for OSA followed by actigraphy:

Subjects will be asked to monitor their sleep using sleep logs during one week. On the first night, OSA will be monitored using a WatchPAT (*Itamar Medical, Tel Aviv, Israel*) (Figure 8). We have experience using WatchPAT in AAs with very low failure rate (less than 1%). This self-applied device measures peripheral arterial volume changes using a finger-mounted plethysmograph. The information is collated

CONFIDENTIAL

This material is the property of the NYU School of Medicine and Langone Medical Center. Do not disclose or use except as authorized in writing by the study sponsor

with pulse oximetry and is further analyzed using an automated algorithm. This algorithm associates arousals with measurement of O₂Sat to determine respiratory effort-related arousals showing excellent sensitivity and specificity for identification of OSA, defined as AHI4% \geq 5 on full NPSG²²⁴. After automated analysis, all raw data and results are reviewed by [name]. Only subjects with an AHI4% $<$ 15 and AHI4% $>$ 5 with Epworth $<$ 10 will be invited to participate. Those cases with suspicion of OSA will be reviewed by [name] and [name]. If OSA is confirmed, they will be excluded and referred to a sleep specialist. Actigraphs (AMI, Ardsley, NY) (Figure 9) with off-wrist detection and a sleep diary will be provided to the subjects to use for the 7 days following the use of the WatchPAT. The purpose will be to record the sleep-wake cycle and provide estimates of total sleep time (TST) in the home. Actigraph will also provide bedtimes and wake times for NPSG N1-N2 in accordance with their usual sleep habits.

Figure 8.
WatchPAT

Figure 9. Actigraph

Measurement of Slow Wave Sleep (SWS) characteristics using NPSG:

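### The OSA eligibility rule is stated inconsistently in the Summary and sections 4, 4.2 and 6.1, and no single reading of its 'and' makes them agree

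*Combined protocol and SAP*

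**What the plan says.** The rule appears in four places in the combined protocol and SAP.

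- **Section 4.2, Exclusion Criteria.** The list opens with "An individual who meets any of the following criteria will be excluded from participation in this study". One of its bullets is "OSA (defined as AHI4%>15 and AHI4%>5 with Epworth" of at least 10. The list is any-of, but the *and* sits inside this one bullet.
- **Section 4, Study Enrollment and Withdrawal (Subjects).** The same two limbs are joined by the same word: "OSA (defined as $AHI_4\% > 15$ and $AHI_4\% > 5$ with $Epworth" of at least 10.
- **Section 6.1, home monitoring for OSA.** "Only subjects with an AHI4% $<$ 15 and AHI4% $>$ 5 with Epworth $<$ 10 will be invited to participate". Suspected cases are then reviewed individually, and confirmed cases are excluded and referred. The only definition of OSA in that paragraph is AHI4% of 5 or more on full polysomnography.
- **Protocol Summary.** People in the total-sleep-time range with "absence of moderate to severe OSA will be invited to perform a 2-night nocturnal polysomnography". There is no Epworth condition and no numeric threshold.

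Section 4.4 gives the only planning figures tied to the rule: 270 enrolled to reach 210 eligible, with 17% referred because of OSA and 3–5% lost for other reasons.

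**The concern.** An eligibility criterion has to give the same answer whoever applies it. Here the answer depends on how *and* is read and on which section is open. Taken literally, section 4.2 lets in people whom the Summary bars, and section 6.1 turns away people with the least apnea.

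This bears on the aims. Section 2.1 says that frequent apnea impairs entry into slow wave sleep, which is the exposure, and that OSA is generally more prevalent in African Americans, who form one side of the race comparison. Under Aim 3, section 3.1 criticises earlier studies for including OSA patients. Section 3.1 also promises adjustment for AHI4% in Aim 2, but the regression blocks for hypotheses 2 and 3 in section 9.3 do not list AHI. The eligibility rule therefore carries much of the protection against confounding by OSA for the primary endpoint. Protocol deviations under section 12.3 also cannot be judged against rules that conflict.

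**Working it through.** **1. The plan's own flow.** Section 4.4: 270 × (1 − 0.17 − 0.03) = 216.0 and 270 × (1 − 0.17 − 0.05) = 210.6. The target of 210 is reproduced at the upper loss rate.

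**2. Each reading applied to ten profiles** (AHI4% of 3, 5, 10, 15, 20; Epworth of 6, 12). The last column reads section 6.1 as AHI4% below 15 and, *where AHI4% is above 5*, Epworth below 10. The italic condition is not in the text.

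| AHI4% / Epworth | 4.2, both limbs needed | 6.1, both limbs needed | 4.2, either limb excludes | 6.1, either limb invites | 6.1 with added condition |
|---|---|---|---|---|---|
| 3 or 5 / 6 or 12 (four profiles) | not excluded | not invited | not excluded | invited | invited |
| 10 / 6 | not excluded | invited | not excluded | invited | invited |
| 10 / 12 | not excluded | not invited | excluded | invited | not invited |
| 15 / 6 | not excluded | not invited | not excluded | invited | not invited |
| 15 / 12 | not excluded | not invited | excluded | not invited | not invited |
| 20 / 6 | not excluded | not invited | excluded | invited | not invited |
| 20 / 12 | excluded | not invited | excluded | not invited | not invited |

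- *And* as a conjunction in both sections: they disagree in 8 of 10 profiles. The limb with AHI4% above 5 adds no AHI restriction in section 4.2, which reduces to AHI4% above 15 with Epworth of at least 10.
- *And* as a list of alternatives in both sections: profiles 10/12 and 20/6 are excluded and invited at once.
- Alternatives in section 4.2, conjunction plus the unwritten condition in section 6.1: agreement everywhere except 15/6, which is neither excluded nor invited.

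**3. Against the Summary.** Assume that moderate-to-severe means AHI4% above 15; the documents give no number. Profile 20/6 is barred by the Summary but admitted by the literal section 4.2. Profile 10/12 passes the Summary but is excluded if either limb of section 4.2 excludes.

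**4. Against section 4.4, without any prevalence.** The flow allows 270 − 210 = 60 losses. OSA takes 270 × 0.17 = 45.9 and other losses take 270 × 0.03 = 8.1 to 270 × 0.05 = 13.5, together 54.0 to 59.4. That leaves 0.6 to 6.0 people to be turned away for AHI4% of 5 or less. The literal section 6.1 rule would also need 210/270 = 77.8% of enrolees to lie strictly between 5 and 15 with Epworth below 10.

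**5. Illustration with the prevalences in section 2.1** (20% mild, 6.6% moderate-to-severe). These are for healthy adults, and the section says that incidence is higher in the elderly. Assume mild is AHI4% of 5 to 15, and let p be the share with Epworth of at least 10, equal in both severity groups. The documents do not give p.

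- Literal section 4.2 excludes 6.6p: 0.66% at p = 0.1, 3.3% at 0.5, 6.6% at 1.
- Either-limb section 4.2 excludes 6.6 + 20p: 8.6%, 16.6%, 26.6%. It equals the planned 17% at p = (17 − 6.6)/20 = 0.52.
- The two readings differ by 6.6 + 13.4p people per 100: 7.9, 13.3, 20.0.
- Literal section 6.1 turns away 100 − 20(1 − p): 82%, 90%, 100%. This includes the 100 − 20 − 6.6 = 73.4% without OSA.

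**The case against.** The strongest reply is that this is loose drafting with an obvious meaning. As a strict conjunction, the lower threshold in section 4.2 is redundant, so the author must have meant two excluded groups. The Summary rules out admitting people with moderate-to-severe disease, and the recruitment plan rules out rejecting everyone at 5 or less. On that view only AHI4% of exactly 15 with Epworth below 10 is left open.

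Much of this stands: the intent is probably recoverable. But recovering it requires *and* to mean *or* in section 4.2, to remain *and* in section 6.1, and a condition that nobody wrote. The Summary would still lack the Epworth limb.

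There are also safeguards: the ARES questionnaire at pre-screening, the case review in section 6.1, and AHI as a covariate for hypothesis 1.1. AHI could also enter the Aim 2–3 models through the section 9.3 clause that adds covariates differing between the groups. These are real but partial. The case review names no exclusion threshold, and the only definition near it, AHI4% of 5 or more, would remove non-sleepy mild cases whom the preceding rule invites.

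A reader might infer more than the documents support:

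- *That the rule admits most OSA cases.* With OSA taken as AHI4% above 5, literal section 4.2 admits at least 20/26.6 = 75%. But that uses healthy-adult prevalences and counts non-sleepy mild cases, whom the two-group reading also admits.
- *That the rule defeats the aim of avoiding confounding by OSA.* This ignores the safeguards above.
- *That 73% of candidates will be turned away.* That follows only from a literal reading which section 4.4 contradicts, with prevalences from another population.

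**Conclusion.** The point holds as an inconsistency in a stated eligibility threshold. Literal section 4.2 admits non-sleepy people with AHI4% above 15, contrary to the Summary. Literal section 6.1 turns away everyone at 5 or less, which the 17% referral and the 270-to-210 flow cannot accommodate. AHI4% of exactly 15 with Epworth below 10 is unassigned, both literally and on the most charitable reading.

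The logical findings (8 of 10 profiles in conflict, at most 6 people of slack in the flow) need no outside figures. The Summary comparison assumes that moderate-to-severe begins above 15. The population shares (about 13 per 100 between the two readings of section 4.2 at p = 0.5) are illustrations that rest on healthy-adult prevalences and an assumed Epworth rate.

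The documents do not show that the wrong people have been or will be enrolled. They show that the text does not fix who should be.

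**What to change.** Reconcile the Summary, section 4, section 4.2 and section 6.1 into one explicit logical statement used in all four places. It should:

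1. state the connector between the limbs, so that *and* no longer carries two meanings;
2. make the invitation rule in section 6.1 the exact complement of the exclusion rule, so that every combination of AHI4% and Epworth is either invited or excluded and none is both;
3. assign the boundary value of 15;
4. say which definition of OSA the case review in section 6.1 applies.

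The thresholds and the connector are the sponsor's decision. If enrolment has begun, the sponsor should document which rule was applied. The cost is a wording amendment in four places, with no new procedure or measurement.
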